### 1.3 Treatments

The study product will be Test Dentifrice which is Dentifrice containing 5% w/w KNO3, 1% alumina, 5% STP and 1150ppm fluoride as sodium fluoride and Reference product will be Dentifrice containing 1150ppm fluoride as sodium fluoride. Subjects will brush for two timed minutes twice daily (morning and evening).

### 1.4 Sample Size Calculation

There were no previous directly comparable studies that have evaluated the effect of dentifrice on maintaining tooth whiteness after peroxide bleaching upon which to base an estimate of sample size. However, based on a previous study evaluating the tooth whitening abilities of the test dentifrice ([Haleon Clinical Study 300024, 2023](#)), a mean change (SD) of VITA scores of 1 ( $\pm 2$ ) was assumed. Sufficient individuals will be screened to enroll approximately 160 subjects (approximately 80 per group) assuming an estimated 20% dropout rate; approximately 128 completed subjects (approximately 64 per group) are deemed sufficient to detect a difference between the Test and Reference Dentifrices at 24 weeks with 80% power.

## 2 Planned Analyses

### 2.1 Interim Analysis

No interim analysis is planned for this study.

### 2.2 Final Analyses

The final planned primary analyses will be performed after the completion of the following sequential steps:

1. All subjects have completed the study as defined in the protocol.
2. All required database cleaning activities including any external data reconciliation have been completed and database has been locked.
3. All criteria for unblinding the randomization codes have been met and the randomization codes have been distributed.

### **3 Considerations for Data Analyses and Data Handling Conventions**

#### **3.1 Baseline Definition**

There will be no change-from-baseline assessments done for this study.

#### **3.2 Subgroups/Stratifications**

Subjects who satisfy all selection criteria will be randomized into the study. Randomization numbers will be assigned in ascending numerical order as each subject is determined to be fully eligible.

Subjects will be stratified based on clinically diagnosed DH status (Yes/No). The stratification factor will give rise to two strata.

- **Stratum 1:** Dentine Hypersensitivity Present
- **Stratum 2:** Dentine Hypersensitivity Not Present

With each stratum, subject will be randomized to Test Dentifrice and Reference Dentifrice with 1:1 allocation ratio.

In the event of mis-stratification, the correct strata according to CRF information will be used in the analysis (i.e., derived stratification variable from ADSL will be used for analysis).

#### **3.3 Centers Pools**

Since this is single center study, pooling of centers is not applicable.

#### **3.4 Timepoints and Visit Windows**

The timepoints and visits for this study are defined in “Schedule of Activities” defined in section 1.2 of study Protocol (v2.0 dated 13-Nov-2023). Any deviation from the study schedule may be reviewed on case-by-case basis at the Blinded Data Review Meeting (BDRM) to determine whether the data should be excluded from the Per-Protocol (PP) analyses.

### **4 Data Analysis**

Data analysis will be performed by CCI with oversight from Haleon. The statistical analysis software used will be SAS version 9.4 or higher.

Prior to database closure a BDRM will be conducted in which various aspects of the trial will be discussed and agreed.

One aspect that will be considered prior to or during the BDRM is the assessment of the number of subjects who have dropped or discontinued from the study due to pandemic related events

and the potential need of a sensitivity analysis. Any major changes to planned analyses will need an amendment to SAP.

Except as described below, all listings will be produced for all randomized subjects.

## 4.1 Populations for Analysis

Tables described in this section will be produced for all randomized subjects.

### 4.1.1 Subject Disposition

Screen failures are defined as subjects who consent to participate in the clinical study but are not subsequently randomized. An enrolled subject is a subject who has signed informed consent and is eligible to proceed beyond the screening visit.

The number of subjects screened, enrolled, and randomized will be presented in Table 14.1.1.

The number and percentage of screen failure subjects (subjects not randomized) with reasons why subjects are not will be displayed. Percentages for screen failure subjects will be based on the total number of subjects screened.

The number and percentage of randomized subjects who complete and discontinue the study, broken down by reason for discontinuation by study product and overall will also be displayed. The percentages will be based on the number of subjects randomized.

Table 14.1.1 will also present the number and percentage of subjects in each of the defined analysis populations (as defined in [Section 4.1.3](#)) by study product and overall. Percentages will be based on the number of subjects randomized.

Subject disposition including demographic data (age, sex, race and ethnicity), screening date, study product start date and time, subject status (completer, Yes/No), study completion /withdrawal date, duration (in days) in the study (defined as [(date of completion or withdrawal – start date of study product) + 1], and the primary reason for withdrawal will be listed (Listing 16.2.1.1) by study product for all randomized subjects.

Subject disposition information will be listed for non-randomized subjects (Listing 16.2.1.2), displaying subject number, demographic information (age, sex, race and ethnicity), screening date, reason for screen failure and any further details of reason for screen failure and discontinuation status.

### 4.1.2 Protocol Deviations

Protocol deviations will be tracked by the study team throughout the conduct of the study. Data will be reviewed prior to unblinding and closure of the database to ensure all important deviations are captured and categorised. Subjects with important protocol deviations liable to influence the efficacy outcomes will have affected data excluded from the PP analyses. Subjects may also be identified as having important protocol deviations not leading to exclusion of data from the PP analyses.

Important deviations of the protocol procedures may include, but will not necessarily be limited to the following:

- Consent procedures
- Inclusion/Exclusion criteria
- Study procedures
- Randomization procedures
- Non-compliance with product administration
- Inadmissible concomitant medication
- Visit schedule/interval
- Other

The specific details of the important protocol deviations will be listed in Protocol Deviation Management Plan and assessment process will be specified in the Blind Data Review Plan and subjects with important protocol deviations will be identified at the BDRM.

The number and percentage of subjects with at least one important protocol deviation, at least one important protocol deviation not leading to exclusion of data from PP analyses (overall and by each deviation reason) and at least one important protocol deviation leading to exclusion of data from the PP analyses (overall and by each deviation reason) will be presented by study product (Table 14.1.2) and listed in Listing 16.2.2.1.

All protocol deviations collected on the protocol deviation case report form page will be listed in Listing 16.2.2.2. The listing will present date of deviation, type of deviation, and deviation description.

#### 4.1.3 Analysis Populations

Analysis populations are defined as

Population	Definition / Criteria	Analyses Evaluated
Safety	Comprise of all randomized subjects who complete at least one use of study product. This population will be based on the product the subject actually received*. Any subject who receives a randomization number will be considered to have been randomized.	Demographics Safety
Modified Intent-To-Treat (mITT)	Comprise all randomized subjects who complete at least one use of study product and have at least one assessment of tooth color after the bleaching period.	Demographics Compliance Efficacy Analysis Exploratory Analysis

Population	Definition / Criteria	Analyses Evaluated
	This population will be based on the study product to which the subject was randomized. Any subject who receives a randomization number will be considered to have been randomized.	
Per-Protocol	Comprise all subjects in the mITT population who have at least one assessment of efficacy considered unaffected by protocol violations. Protocol deviations that may exclude subjects from the PP population are defined in Section 4.1.2 (Protocol Deviations) . This population will be based on the study product to which the subject was randomized.	Efficacy Analysis
Repeatability Population	Tooth Color Repeatability Population: subjects who have at least one repeat tooth color clinical assessment at any visit. MLSI Repeatability Population: Subjects who have at least one repeat MLSI clinical assessment at any visit.	Repeatability Assessment Analysis

NOTES:

\* The treatment actually received will be assumed to be the same as the randomized treatment unless a protocol deviation is recorded to indicate that incorrect treatment was dispensed to the subject.

Please refer to [Appendix 1](#): List of Data Displays which details the population to be used for each display being generated.

The numbers of subjects included in each of the analysis populations, will be summarized (Table 14.1.1). Subjects excluded from any of the analysis populations will be listed in Listing 16.2.3.1.

The primary population for assessment of efficacy will be the mITT Population. A PP analysis will be performed on the primary endpoint only if more than 10% of mITT subjects are excluded from the PP Population. A decision on whether a PP analysis will be performed will be made prior to study unblinding (release of the randomization codes).

## 4.2 Subject Demographics and Other Baseline Characteristics

Demographic and baseline characteristics summaries will be produced for Safety and mITT Population.

#### **4.2.1 Demographic Characteristics**

Descriptive statistics (number of subjects [n], mean, standard deviation [SD], median, minimum and maximum for continuous variables and frequency count [n] and percentage [%] of subjects for categorical variables) will be presented for demographic variables by study product. These variables include age, sex, race, ethnicity, and stratification group and will be presented for the Safety population (Table 14.1.3.1), and the mITT population (Table 14.1.3.2).

Demographic information will be listed (Listing 16.2.4.1) for all randomized subjects.

#### **4.2.2 General Medical History**

Medical and surgical history (in the last year) including allergies or drug sensitivity will be listed in Listing 16.2.4.2, with start date and end date or ongoing at the start of study product

### **4.3 Treatments (Study Product, Rescue Medication, other Concomitant Therapies, Compliance)**

Randomization details will be listed, including the randomization number, stratification group, the planned study product, the actual study product the subject was randomized to and the randomization date (Listing 16.1.7.1) for all randomized subjects.

The study product kit allocations will be listed (Listing 16.1.7.2), including kit number and study product information.

#### **4.3.1 Study Product Compliance and Exposure**

Compliance data will also be summarized for the mITT population and will be assessed by number of brushings.

Number of brushings, brushing compliance (%), number of missed brushings, number of additional brushings will be summarized using descriptive statistics as separate categories by study product in Table 14.2.1.1 by cumulative visit.

Number of brushings is defined as: [(date of Visit N – date of Visit 1) multiplied by 2 – number of missing brushings + number of additional brushings].

Brushing compliance (%) is defined as: [100 x (Number of brushings / Expected number of brushings)], where expected number of brushings is defined as: [(date of Visit N – date of Visit 1) multiplied by 2].

Study product compliance (number of brushings / brushing compliance [%] / number of missed brushings / numbers of additional brushings) will be listed in Listing 16.2.5.1 for all randomized subjects by study product.

#### **4.3.2 Bleaching Compliance and Exposure**

Bleaching Compliance will be summarized for mITT Population where number of bleaching, bleaching compliance (%) and missed/additional bleaching occurrence will be summarized using descriptive statistics as separate categories by study product in Table 14.2.1.2 by cumulative visit.

Number of bleaching is defined as: [(date of Visit 3 – date of Visit 2) – number of missing bleaching + number of additional bleaching].

Bleaching compliance (%) is defined as: [100 x (Number of bleaching / Expected number of bleaching)], where expected number of bleaching is defined as: (date of Visit 3 – date of Visit 2).

Bleaching compliance (number of bleaching / bleaching compliance [%] / number of missed bleaching / numbers of additional bleaching) will be listed in Listing 16.2.5.2 for all randomized subjects by study product.

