### 6.1.3 Dosage Form and Packaging

The study products are dentifrices, intended for topical oral use, and will be applied by toothbrushing using a manual toothbrush.

The experimental dentifrice will be manufactured and filled into plain white tubes by the sponsor; the reference dentifrice will be supplied in its commercial pack and sourced from the market the study is performed in (USA). All study dentifrices will be overwrapped in white vinyl (to mask their identity and obscure the branding of the marketed product) with a study label affixed. The content of the product labels will be in accordance with all applicable regulatory requirements and will be the responsibility of the sponsor's Global Clinical Supplies Group. Each study label will contain, but not be limited to, protocol number, directions for use and storage requirements.

Each subject will receive sufficient tubes of their assigned study dentifrice for usage during the 24-week treatment period. Sundry items (including the peroxide bleaching treatment) will be supplied in their commercial packaging for dispensing by study staff as specified in [Table 6.2](#).

Care should be taken with the supplied products and their labels so that they are maintained in good condition. It is important that all labels remain intact and legible for the duration of the study. Subjects should be instructed to not remove or deface any part of the study label.

All products supplied are for use only in this clinical study and should not be used for any other purpose.

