#### **12.3.4 Safety Analyses**

The Safety population will be used for safety analyses. Safety analyses will be performed according to study product received.

Safety analyses will focus on:

- Exposure and compliance with study product
- Adverse Events (AEs)

All AEs will be reviewed by the Clinical Research Scientist, or designee, prior to database lock and unblinding and will be coded using the MedDRA. During this review stage, AEs will be further categorized as oral or non-oral. AEs will be regarded as ‘treatment’ emergent if they occur on or after the first use of study product at the Baseline visit.

The following AEs summaries (number of distinct AEs and frequency/proportion of subjects affected will be presented by study product group and overall:

- Treatment emergent AEs
- Treatment emergent AEs by System Organ Class (SOC) and Preferred Term (PT);
- Treatment emergent AEs by Oral/Non-Oral and PT;
- Treatment emergent treatment related AEs by Oral/Non-Oral and PT;
- Treatment emergent treatment related serious AEs by SOC and PT

A listing of all AEs will be presented for all subjects in the Safety population. Separate listings will be presented for any deaths, serious AEs and AEs leading to study or product discontinuation.

A list of medical device incidents will also be included as part of the safety analyses. No specific risks or anticipated adverse device effects are expected to be observed within this study, however all AEs and medical device incidents will be assessed to evaluate the tolerability and safety of the treatments.

No specific risks or anticipated adverse device effects are expected to be observed within this study, however all AEs and medical device incidents will be assessed to evaluate the tolerability and safety of the treatments.

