## **5 Changes to the Protocol Defined Statistical Analysis Plan**

There were no changes or deviations to the originally planned statistical analysis specified in the protocol amendment (Dated: 13-Nov-2023).

<Compound/Product>

<Protocol Number>

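### The SAP summarises dentifrice exposure and compliance only in the mITT, where the protocol makes it a Safety-population analysis, and SAP section 5 does not declare the change

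*SAP*

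**What the plan says.** **Protocol.** Section 12.3.4 states "The Safety population will be used for safety analyses", with subjects grouped by product received. Of the two items it says these analyses will focus on, the first is "Exposure and compliance with study product". Section 6.1.3 fixes what that covers: "The study products are dentifrices, intended for topical oral use". The same section places the peroxide kit elsewhere: "Sundry items (including the peroxide bleaching treatment) will be supplied in their commercial packaging". Sections 12.3.8.1 (brushing) and 12.3.8.3 (bleaching, under Other Therapy) ask for descriptive compliance summaries and name no population.

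**SAP.** The table in 4.1.3 gives the Safety population demographics and safety, and gives compliance to the mITT, which is analysed as randomised. To enter the mITT a subject must "have at least one assessment of tooth color after the bleaching period". Section 4.3.1 says: "Compliance data will also be summarized for the mITT population and will be assessed by number of brushings". Section 4.3.2 says: "Bleaching Compliance will be summarized for mITT Population where number of bleaching, bleaching compliance (%) and missed/additional bleaching occurrence will be summarized". Appendix 1 lists Tables 14.2.1.1 (brushing) and 14.2.1.2 (bleaching) for the mITT, with no Safety version of either. Listings 16.2.5.1 and 16.2.5.2 give the individual data for all randomised subjects. Section 5 says: "There were no changes or deviations to the originally planned statistical analysis".

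**The concern.** Dentifrice exposure is the natural companion to the adverse event tables: it tells the reader how much product was used by the people whose events are counted. Under the SAP the two rest on different sets of people. Anyone who used the dentifrice and left before a post-bleach shade score is in the adverse event tables and absent from every exposure or compliance summary.

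If those subjects brushed less consistently than the rest, the summarised compliance is too high. The protocol specified the summary on the Safety population, and a reader of SAP section 5 would believe nothing had moved. Sections 4.3.1 and 4.3.2 also carry exposure in their headings, yet neither defines a separate exposure measure such as days on product.

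**Working it through.** **1. Figures in the plan.** No stated figure bears directly on this point. The only related one is the 20% dropout: 160 × 0.20 = 32 subjects, or 16 per arm if split evenly. The documents do not say when those exits occur.

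**2. The two documents side by side.**

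| Item | Protocol | SAP |
|---|---|---|
| Dentifrice exposure and compliance | Safety population (12.3.4) | mITT (4.1.3, 4.3.1, Appendix 1) |
| Grouping | Product received | Product randomised |
| Bleaching compliance | No population named (12.3.8.3) | mITT (4.3.2, Appendix 1) |
| Departure declared | n/a | None (section 5) |

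The first two rows conflict. The third does not.

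**3. Who is in the Safety population but not the mITT.**

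- *Subjects discontinued at Visit 2.* Subjects are randomised and brush under supervision at Visit 1 (protocol 8.1). Inclusion criterion 6b requires a mean shade of at least 13 at Visit 1 and again at Visit 2, and 8.2.1 step 6 discontinues those who no longer qualify. They have used the dentifrice for 2 weeks ± 2 days, that is 12 to 16 days. At two brushings a day this is 24 to 32 expected brushings, 28 at the nominal interval. The SAP 4.3.1 formula needs only the dates of Visit 1 and Visit N, so their compliance can be calculated as the plan stands.
- *Subjects who start the dentifrice and never return for a post-bleach shade score.*

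A subject who stops bleaching but has a shade score at Visit 3, 4 or 5 remains in the mITT.

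**4. Size for brushing.** Let n be the Safety-population subjects in an arm, d the number of them outside the mITT, and C_in and C_out the mean compliance inside and outside it.

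Safety mean = [(n − d) × C_in + d × C_out] / n

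mITT mean − Safety mean = (d / n) × (C_in − C_out)

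With n = 80:

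- d = 0: the gap is 0
- d = 1: 1/80 = 1.25% of the difference C_in − C_out
- d = 4: 4/80 = 5% of it
- d = 16 (every planned dropout in the arm leaving this early): 16/80 = 20% of it

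The documents give neither d nor C_in − C_out. Subjects discontinued at Visit 2 on shade alone need not have brushed less than the others, so their contribution to the gap could be nil.

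**5. Bleaching, as a companion point.** SAP 4.3.2 defines expected applications as the date of Visit 3 minus the date of Visit 2. Without a Visit 3 date the value is undefined, so changing the population label alone would recover none of the subjects who left before Visit 3.

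The possible scale can be shown only by assumption. Suppose 80 per arm start bleaching, d leave having completed b of 7 applications, and the rest complete all of them. The mITT mean is then 100%, and the mean over all who started is [(80 − d) × 100 + d × 100 × b/7] / 80:

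| d | b = 1 | b = 3 |
|---|---|---|
| 0 | 100% | 100% |
| 2 | 97.9% | 98.6% |
| 4 | 95.7% | 97.1% |
| 16 | 82.9% | 88.6% |

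The last row puts the whole 20% dropout into the bleaching week. If dropout were instead uniform over about 2 + 1 + 24 = 27 weeks (also an assumption), about 16/27 = 0.6 subjects per arm would leave in that week.

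**The case against.** The best defence is that this is a population label with little behind it. No efficacy or adverse event result changes. Compliance is commonly read as context for efficacy, and the mITT is a reasonable set for that. Both compliance measures are listed for all randomised subjects, and Listing 16.2.1.1 gives product start date and days in study for the same set. The received-versus-randomised distinction has effect only where a deviation records that the wrong product was dispensed (SAP 4.1.3, note to the table).

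That argument stands as to impact, which is minor. It does not remove the mismatch. A listing is not a summary, and the protocol placed this item among the Safety-population analyses. The word *also* in SAP 4.3.1 might suggest that a Safety version exists as well, but Appendix 1 contains none.

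A reader might infer two stronger things that the documents do not support:

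- *That SAP 4.3.2 contradicts protocol 12.3.4.* It does not. That item covers the study product, which is the dentifrice. The peroxide kit is a sundry item, and protocol 12.3.8.3 leaves the population for bleaching compliance open.
- *That bleaching tolerability is made to look better than it was.* Compliance is not the tolerability measure. The safety and tolerability endpoint is treatment-emergent adverse events, tabulated in the Safety population. Oral soft tissue findings (Table 14.3.4.1) and medication taken for tooth sensitivity (Table 14.3.4.2) are listed in Appendix 1 for the Safety population too. Discontinuations by reason, and the listing of events leading to discontinuation, cover all randomised subjects.

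**Conclusion.** The point holds for the dentifrice. The protocol specifies exposure and compliance with study product in the Safety population by product received; the SAP delivers it only in the mITT by randomised product and declares no change. This rests on the text of the two documents and needs no assumption.

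The consequence is limited. Subjects discontinued at Visit 2, or lost before any post-bleach score, are missing from the only compliance summaries. Mean brushing compliance may be overstated by (d / n) × (C_in − C_out), which the documents do not fix and which may be zero. The primary analysis and the adverse event tables are unaffected. For bleaching there is an unspecified population and a formula that fails without Visit 3, but no contradiction of the protocol, and the percentages shown for it are illustrations only.

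**What to change.** Before unblinding:

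1. Add a Safety-population version of Table 14.2.1.1, by product received, and include days on dentifrice (first to last use). Keep the mITT version as context for efficacy.
2. Add the new table to Appendix 1, amend SAP 4.1.3 and 4.3.1 to match, and record any remaining difference from protocol 12.3.4 in SAP section 5.
3. For bleaching compliance, state the intended population and the reason. If early leavers are to be counted, summarise it for all subjects who started bleaching, leaving out those discontinued at Visit 2 before bleaching. Derive applications from diary counts up to last use, since the present formula needs a Visit 3 date.

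The first two items cost one extra table, from data already planned for listing in all randomised subjects, and some SAP wording. The third, if adopted, needs one new derivation.
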